## 9.2.5 SAEs (Including Deaths) and Adverse Events Leading to Study Drug Discontinuation

SAEs (including deaths) and AEs leading to study drug discontinuation will be summarized by SOC and PT and in listing format.

#### 9.2.6 Adverse Events of Special Interest

The AESI categories will be identified by the search criteria per Standard MedDRA Queries (SMQs)/Company MedDRA Queries (CMQs) specified in Appendix B.

[figure not shown]
Treatment-emergent Adverse events of special interest will be summarized by SOC and PT and listing format. Additionally, AESI rates per 100 patient years of exposure will be provided for each AESI category (Appendix B) in the AE overview summary.

#### 9.3 Analysis of Laboratory Data

Data collected from central and local laboratories, including additional laboratory testing due to an SAE, will be used in all analyses, except for Baseline where SAE-related laboratory assessments on or before the first dose of study drug will be excluded. The clinical laboratory tests defined in the protocol (e.g., hematology and clinical chemistry) will be summarized.

#### **Analysis of Quantitative Laboratory Parameters**

Each laboratory variable will be summarized for all time points (starting with Baseline) with the number of non-missing observations, mean and standard deviation, median, minimum and maximum. Mean change from Baseline to each applicable post-baseline visit will be summarized for selected laboratory variables, with the number of observations, baseline mean, and visit mean. The change from baseline mean, standard error, and 95% confidence interval will be presented for the mean change from Baseline within each treatment group.

For SA1 population, treatment group differences between upadacitinib treatment group and placebo group for changes from Baseline will be analyzed using a one-way Analysis of Variance (ANOVA) model with treatment as a fixed factor and 95% CI for treatment difference will be presented for selected laboratory parameters.

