8.1.8.3 Analysis of Laboratory and Vital Sign Data

Changes from Baseline to minimum value, maximum value and final values in continuous laboratory and vital sign parameters will be summarized by treatment group. Treatment group differences for mean changes from Baseline will be analyzed using ANOVA.

Vital signs and laboratory data will be described by statistical characteristics and frequency of abnormal values. Frequencies and percentages of subjects with laboratory shifts from Baseline to the final values using normal ranges to define categories (low, normal, high, and missing) will be summarized by the respective categories. Values beyond the normal values will be listed. Low or high laboratory values will also be flagged in the data listings. Analysis details will be specified in the SAP.

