## 9.0 Safety Analyses

#### 9.1 General Considerations

Safety analyses will be performed on the safety populations in the 8-week DB induction period (Part 1, SA1 population) and the 8-week OL extended treatment period (Part 2, SA2 population). In addition, safety summaries will be provided on the all upadacitinib treated safety population (SA-UPA).

The standard safety analyses will include reporting of adverse events (AEs), adverse events of special interest (AESIs), laboratory, and vital signs measurements. Frequency tables and exposure adjusted event rate per 100 patient-years tables of subjects with

treatment-emergent adverse events (TEAEs) by system organ class (SOC) and by preferred term (PT) as in the Medical Dictionary for Regulatory Activities (MedDRA) dictionary will be provided by treatment group. All continuous laboratory parameters and vital signs variables at each visit will also be summarized by treatment group. Frequency tables of subjects meeting criteria for potentially clinically important vital sign values and for potentially clinically important laboratory values will be provided by treatment group.

The Baseline for safety analysis will be treatment dependent. For SA1 population, laboratory and vital signs measurements, the Baseline value is defined as the last available measurement before study drug administration for each subject. For SA2 and SA-UPA populations, the Baseline value is defined as the last available measurement before first dose of upadacitinib.

Missing safety data will not be imputed.

[figure not shown]

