#### 9.4 Analysis of Vital Signs

Vital sign measurements of systolic and diastolic blood pressure, pulse rate, body weight, respiratory rate and body temperature will be summarized.

Each vital sign variable will be summarized for all time points (starting with Baseline) with the number of non-missing observations, mean and standard deviation, median, minimum and maximum. Mean change from Baseline to each applicable post-baseline visit will be summarized for each vital sign variable, with the number of observations, Baseline mean, and visit mean. The change from Baseline mean, standard error, and 95% confidence interval will be presented for the mean change from Baseline within each treatment group.

For SAh1 population, treatment group differences between upadacitinib treatment group and placebo group for changes from Baseline will be analyzed using a one-way Analysis of Variance (ANOVA) with treatment as a fixed factor and 95% CI for treatment difference will be presented for each vital sign variable.

Vital sign variables will be evaluated based on potentially clinically important (PCI) criteria (Appendix C). For each vital sign PCI criterion, the number and percentage of subjects who have a vital sign value meeting the criteria will be summarized. Listings will be provided to summarize subject-level vital sign data for subjects meeting PCI criteria.

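### The SA1 laboratory and vital-sign comparisons subtract baseline but do not adjust for it, so their 95% intervals are generally somewhat wider than ANCOVA would give

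*SAP*

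**What the plan says.** In SAP 9.3 (Analysis of Quantitative Laboratory Parameters), the comparison in SA1 concerns "treatment group differences between upadacitinib treatment group and placebo group for changes from Baseline". The model is a "one-way Analysis of Variance (ANOVA) model with treatment as a fixed factor", and the output is that a "95% CI for treatment difference will be presented for selected laboratory parameters". The selected parameters are not named.

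SAP 9.4 uses the same model for vital signs: "one-way Analysis of Variance (ANOVA) with treatment as a fixed factor and 95% CI for treatment difference will be presented for each vital sign variable". Its label for the population is misprinted but evidently means SA1.

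Protocol 8.1.8.3 agrees: "Treatment group differences for mean changes from Baseline will be analyzed using ANOVA". It names no covariate.

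The baseline value is defined in SAP 9.1: for SA1, "the Baseline value is defined as the last available measurement before study drug administration for each subject". The laboratory tables also report mean change "with the number of observations, baseline mean, and visit mean".

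The continuous efficacy model differs. The MMRM in SAP 8.3.2 carries the baseline measurement as a continuous covariate.

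**The concern.** A subject with a high baseline value tends to fall at the next visit, and one with a low value tends to rise. Change is therefore usually negatively correlated with baseline, and a model with treatment alone leaves that predictable variation in the residual. Subtraction also assumes a slope of exactly 1 for post-baseline on baseline. If the true slope β is not 1, a chance difference between the arms at baseline is only partly cancelled.

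The stake is the precision of the SAP's between-arm estimates of mean laboratory and vital-sign change. Safety is part of the study's primary objective. Every change score already needs a baseline value, so adjusting for it would lose no subject.

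**Working it through.** **Inputs from the documents.** Arm sizes are 154 placebo and 308 upadacitinib (SAP 2.4), and the intervals are 95%. The plan gives no figure for the width or precision of these intervals, so there is none to reproduce. Its one related figure, power above 95% for the primary endpoint, does reproduce: exact two-sided Fisher power at 154/308 with 5% versus 18% is 98.9%. That bears only on the arm sizes. Actual numbers per comparison may be lower, because missing safety data are not imputed, but the width ratios below do not depend on n.

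**Assumed inputs.** The documents give neither ρ, the baseline-to-post correlation, nor k = SD_post/SD_base. I take ρ from 0.3 to 0.9 and k from 0.8 to 1.25.

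**Equal SDs (k = 1, common SD σ).**
- Residual variance of ANOVA on change: 2σ²(1−ρ).
- Residual variance of ANCOVA: σ²(1−ρ²).
- Width ratio, ANOVA to ANCOVA: √(2/(1+ρ)).
- Standard-error factor: √(1/154 + 1/308) = 0.0987. Times 1.96, this is 0.193.

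Half-widths in units of σ are 0.193·√(2(1−ρ)) for ANOVA and 0.193·√(1−ρ²) for ANCOVA:

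| ρ | ANOVA on change | ANCOVA | ANOVA wider by |
|---|---|---|---|
| 0.3 | 0.229 | 0.185 | 24% |
| 0.5 | 0.193 | 0.168 | 15.5% |
| 0.7 | 0.150 | 0.138 | 8.5% |
| 0.8 | 0.122 | 0.116 | 5.4% |
| 0.9 | 0.087 | 0.084 | 2.6% |

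**Unequal SDs.** The width ratio is √[(1 + k² − 2ρk) / (k²(1−ρ²))].
- k = 0.8: ANOVA is 25% to 41% wider over the same range of ρ.
- k = 1.25: ANOVA is 0% to 13% wider.
- The two coincide when ρk = 1, for example ρ = 0.8 with k = 1.25.

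**Simulation.** With 154 versus 308 subjects, equal SDs and 3,000 runs per value, mean width ratios at ρ = 0.5, 0.7 and 0.9 were 1.154, 1.084 and 1.025, matching the formula. Both estimators averaged within 0.002 SD of the true zero difference. Coverage was between 94% and 95% for both.

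**Baseline imbalance.** With β = ρk, an observed baseline difference D between the arms shifts the change-score difference by (β−1)D, so the fraction (1−β) carries through with reversed sign. As an illustration, take ρ = 0.6, k = 1 and an imbalance of 2 standard errors:
- D = 2 × 0.0987 = 0.197 SD.
- Size of shift = 0.4 × 0.197 = 0.08 SD, against a half-width of 0.173 SD.
- Given that imbalance, the estimate has standard error 0.8 × 0.0987 = 0.079 SD, and coverage is about Φ((0.173−0.079)/0.079) = Φ(1.19), or 88%.

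An imbalance of at least that size arises by chance for about 1 variable in 20. SAP 9.4 alone compares six vital signs.

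**The case against.** The best defence is that the plan already uses baseline sensibly. A reader might infer from the one-way model that baseline is ignored. It is not, since the response is change from Baseline. At ρ = 0.8 with equal SDs, the planned half-width is 0.122 SD, against 0.193 SD for a comparison of post-baseline values alone. A reader might also infer that an imbalance passes in full into the estimate, but only the fraction (1−β) does. That defence stands.

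Some variables also get a second model. SAP 3.3 lists change in weight, albumin, total protein, hematocrit and hemoglobin among the additional efficacy endpoints, and SAP 8.6 compares the arms on these by MMRM or ANCOVA. The MMRM is explicitly adjusted for baseline. This stands in part. Those analyses use ITT1, drop data after corticosteroid events and exclude the non-compliant site, so they supplement the safety intervals but do not replace them. For weight at least, the report could carry two treatment differences that disagree partly because only one is baseline-adjusted. The SAP gives no reason for the different modelling.

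It is also true that the safety reading rests on shift tables, CTCAE grades, liver criteria, vital-sign thresholds and events of special interest, none of which would change. No hypothesis or precision target attaches to these intervals. Because the selected laboratory parameters are unnamed, one cannot say that CPK, creatinine or lipids are affected.

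Two costs of ANCOVA are real but small: a documented departure from the protocol, and sensitivity of a common linear slope to extreme baseline values.

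**Conclusion.** The point holds as a modest loss of precision in descriptive safety intervals. With equal SDs and ρ from 0.9 to 0.3, the planned intervals are about 3% to 24% wider than ANCOVA would give. With a smaller post-baseline SD (k = 0.8) the figure reaches 41%, and where ρk = 1 it is nil. These ranges rest on assumed correlations and SDs, so no single figure can be attached to any named parameter.

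A reader might infer that the planned intervals are biased or too narrow. They are not: across repeated randomisations the estimator is unbiased with nominal coverage. Conditional on a sizeable chance imbalance, the estimate is shifted, and ANCOVA would remove that shift. The SAP and protocol agree with each other here, so this is not an inconsistency between them. No primary or ranked endpoint, type I error rate or stated power is affected. It is a free improvement of low priority.

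**What to change.** In SAP 9.3 and 9.4, replace the one-way ANOVA with ANCOVA on change from Baseline, with treatment as the factor and that variable's baseline value as the covariate. Report the adjusted difference with its 95% CI. For strongly skewed analytes such as CPK, if selected, state in advance whether a transformation will be used, which also limits the leverage of extreme baselines. Record the departure from protocol 8.1.8.3 in SAP Section 13, where the SAP already logs changes from protocol analyses.

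The cost is one model term, one degree of freedom and a line in the version history. It needs no new data and loses no subjects.

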#### **Shift Table Analyses**

Changes in laboratory parameters will be tabulated using shift tables categorized as low, normal, or high based on the normal ranges of the laboratory used for each sample. A shift table from Baseline to minimum and maximum value (based on normal range) will be created. A similar shift table will be provided to summarize shifts from Baseline to the final post-baseline value.

#### **Potentially Clinically Significant Laboratory Values**

The criteria for potentially clinically significant laboratory values will be determined by CTCAE criteria of Grade 3, Grade 4 and ≥ Grade 3, with a grade worsening compared to baseline. Toxicity grading scale is based on National Cancer Institute Common Toxicity Criteria (NCI CTC) AE version 4.03. The number and percentage of subjects meeting the criteria for potentially clinically significant laboratory values will be summarized by treatment group. Listings will be provided to summarize subject-level laboratory data for subjects meeting the criteria.

#### **Assessment of Liver Elevations**

The liver-specific laboratory tests include the serum glutamic pyruvic transaminase (SGPT/ALT), serum glutamic-oxaloacetic transaminase (SGOT/AST), alkaline phosphatase (ALP), and total bilirubin (TBL). The frequencies and percentages of subjects with post baseline liver specific function test values that meet the following criteria of potential clinical interest will be summarized by treatment group:

- ALT  $\geq 3 \times ULN$
- ALT  $\geq$  5 × ULN

- ALT  $\geq 10 \times ULN$
- ALT  $\geq 20 \times ULN$
- AST  $\geq$  3 × ULN
- AST  $\geq$  5 × ULN
- AST  $\geq 10 \times ULN$
- AST  $\geq 20 \times ULN$
- TBL  $\geq 2 \times ULN$
- ALP  $\geq 1.5 \times ULN$
- ALT and/or AST  $\geq$  3 × ULN and TBL  $\geq$  1.5 × ULN
- ALT and/or AST  $\geq$  3 × ULN and TBL  $\geq$  2 × ULN,

where ULN is the upper normal limit. The maximum ratio relative to the ULN will be used to determine if subjects meet any of the criteria listed above.

[figure not shown]
A listing of potentially clinically significant liver function laboratory values will be provided. The listing will include all subjects who met any of the following 4 criteria:

- ALT  $\geq 2.5 \times ULN$ , or
- AST  $\geq 2.5 \times ULN$ , or
- ALP  $\geq 1.5 \times ULN$ , or
- TBL  $> 1.5 \times ULN$ .

In addition, eDISH plots will be created displaying post-baseline total bilirubin versus post-baseline ALT, in terms of the maximum ratio relative to the ULN (not necessarily concurrent).

#### 9.4 Analysis of Vital Signs

Vital sign measurements of systolic and diastolic blood pressure, pulse rate, body weight, respiratory rate and body temperature will be summarized.

Each vital sign variable will be summarized for all time points (starting with Baseline) with the number of non-missing observations, mean and standard deviation, median, minimum and maximum. Mean change from Baseline to each applicable post-baseline visit will be summarized for each vital sign variable, with the number of observations, Baseline mean, and visit mean. The change from Baseline mean, standard error, and 95% confidence interval will be presented for the mean change from Baseline within each treatment group.

For SAh1 population, treatment group differences between upadacitinib treatment group and placebo group for changes from Baseline will be analyzed using a one-way Analysis of Variance (ANOVA) with treatment as a fixed factor and 95% CI for treatment difference will be presented for each vital sign variable.

Vital sign variables will be evaluated based on potentially clinically important (PCI) criteria (Appendix C). For each vital sign PCI criterion, the number and percentage of subjects who have a vital sign value meeting the criteria will be summarized. Listings will be provided to summarize subject-level vital sign data for subjects meeting PCI criteria.

## 10.0 Other Analyses

[figure not shown]
No other analyses are planned.

## 11.0 Interim Analyses

There will be no efficacy interim analyses planned for the study.

#### 11.1 Data Monitoring Committee

An external data monitoring committee (DMC) composed of persons independent of AbbVie and with relevant expertise in their field will review unblinded safety data from the ongoing study. The primary responsibility of the DMC will be to protect the safety of the subjects participating in this study.

A separate DMC charter describes the roles and responsibilities of the DMC members, frequency of data reviews, relevant data to be assessed, and general operations.

[figure not shown]
Since there are no efficacy analyses for early stopping, no multiplicity adjustment is needed.

## 12.0 Overall Type-I Error Control

The overall type I error rate of the primary and the ranked secondary endpoints will be strongly controlled using the fixed-sequence multiple testing procedure. Specifically, the testing will utilize the endpoint sequence of the primary and ranked secondary endpoints in the order as specified in Section 3.1 and Section 3.2 at the  $\alpha$  level of 0.05 (two-sided).

No multiplicity adjustment will be applied to the additional efficacy endpoints listed in Section 3.3. The analysis for additional efficacy endpoints will be performed at the nominal  $\alpha$  level of 0.05 (two-sided).

[figure not shown]
Since there are no efficacy analyses for early stopping planned for the DMC review, no  $\alpha$  spending is needed due to the DMC review.

## 13.0 Version History

## Table 1. SAP Version History Summary

Version	Date	Summary		
1.0	17 July 2018	Original version		
2.0	13 July 2020	Revised the SAP per the latest SAP template.		
2.0	13 July 2020	
 
Revised the SAP per the latest SAP template.
 
The following changes have occurred in order to reflect changes in the protocol amendment and regulatory guideline.
 
Updated secondary endpoints: added histologic-endoscopic mucosal improvement, change from baseline in IBDQ total score and change from baseline in FACIT-F score; moved response in IBDQ Bowel Symptom domain, UC-related hospitalizations and surgeries and response in IBDQ fatigue item to other efficacy endpoints.
 
Non-ranked secondary endpoints are now listed under Other Efficacy Endpoints.
 
Added NRI-C method for handling missing data due to COVID-19. NRI-C will be used for the primary efficacy analysis and NRI-NC will be considered as sensitivity analysis.
 
Removed the Last Observation Carried Forward (LOCF) approach from the missing data imputation as LOCF potentially can result in a biased estimation of treatment effect and underestimate the variability.
 
Removed Holm procedure from the multiplicity control method as the number of ranked secondary endpoints was
 
		
		reduced.  Added the bio-IR and non-bio-IR subgroup analysis for the secondary endpoints: endoscopic remission, endoscopic improvement and clinical response per adapted Mayo score.  Remove subgroup analyses including Baseline immunosuppressant use (yes, no), Baseline Adapted Mayo Score (\le median, \rightarrow median), Baseline Full Mayo Score (\le median, \rightarrow median), Baseline hs-CRP (\le median, \rightarrow median), \rightarrow median, \rightarrow media		
3.0	15 September 2020	
 
Added definitions of estimand for primary and key secondary endpoints.
 
Clarified the MI method to handle missing data due to COVID-19 and other reasons.
 
		

[figure not shown]

#### Table 1. SAP Version History Summary (Continued)

Version	Date	Summary		
4.0	05 November 2020	Added supplementary analysis for the primary endpoint to exclude subjects with deviations that could potentially impact the primary analysis.		
5.0	13 November 2020	Added exclusion of subjects from efficacy analysis due to site non-compliance.		
6.0	19 January 2021	Clarified how CIs are derived for the difference in proportions between treatment groups based on the NRI-C approach.		
		Added comparative safety analyses (risk difference and 95% CI) for TEAE overview analysis of SA1 population.		

## **Appendix A.** Protocol Deviations

The number and percentage of subjects who reported at least one of the following protocol deviation categories will be provided.

- Subject entered into the study even though s/he did not satisfy entry criteria.
- Subject developed withdrawal criteria during the study and was not withdrawn.
- Subject received wrong treatment or incorrect dose of study.
- Subject took prohibited concomitant medication.

[figure not shown]

## Appendix B. Definition of Adverse Events of Special Interest

AEs of Special Interest (AESI) will be identified by the following CMQ, SMQ, and other search criteria:

Table B-1. AESI for Upadacitinib with SMQs/CMQs/PTs Searches

AESI	Type of MedDRA Query	Broad or Narrow Search	SMQ/CMQ Search Criteria	
Serious Infections	CMQ		"Infections" – Subset for SAEs	
Opportunistic Infection excluding Tuberculosis and Herpes Zoster	CMQ		"Opportunistic Infection excluding Tuberculosis and Herpes Zoster"	
Active Tuberculosis	CMQ		"Active Tuberculosis"	
Herpes Zoster	CMQ		"Herpes Zoster"	
Neutropenia	CMQ		"Hematological Toxicity – Neutropenia"	
Creatine Phosphokinase (CPK) Elevation	PT		PT of "Blood creatine phosphokinase increased"	
Possible Malignancies	SMQ	Narrow	"Malignancies"	
Malignancy	SMQ	Narrow	"Malignant Tumours"	
Malignancies excluding NMSC	SMQ	Narrow	"Malignant Tumours" removing NMSC output	
Non-Melanoma Skin Cancer (NMSC)	SMQ	Narrow	"Skin Malignant Tumours" removing Melanoma CMQ	
Lymphoma	SMQ	Broad	"Malignant Lymphomas"	
Renal Dysfunction	SMQ	Narrow	"Acute Renal Failure"	
Hepatic Disorder	SMQ	Narrow	"Drug Related Hepatic Disorders – Comprehensive Search"	
Anemia	CMQ		"Non-Hemolytic and Non-Aplastic Anemias"	
Lymphopenia	CMQ		"Hematological Toxicity – Lymphopenia"	
Adjudicated Gastrointestinal Perforation			Based on adjudicated results (the identification of events to be adjudicated are described in the GI Perforation charter)	

[figure not shown]

**Table B-1. AESI for Upadacitinib with SMQs/CMQs/PTs Searches** (Continued)

AESI	Type of MedDRA Query	Broad or Narrow Search	SMQ/CMQ Search Criteria
Adjudicated Cardiovascular Events:	Output from		
MACE*	CAC		
Cardiovascular Death			
Non-fatal Myocardial Infarction			
Non-fatal Stroke			
Undetermined/Unknown Cause of			
Deaths			
Other Cardiovascular events			
Adjudicated Thrombotic Events:	Output from		
VTE**	CAC		
Deep Vein Thrombosis			
Pulmonary Embolism			
Other Venous Thrombosis			
Adjudicated Arterial	Output from		·
Thromboembolic Events	CAC		

CAC = Cardiovascular Adjudication Committee; CMQ = company MedDRA query; PT = preferred term; SMQ = standard MedDRA query

- \* MACE: Major Adverse Cardiovascular Events, defined as cardiovascular death, non-fatal myocardial infarction and non-fatal stroke.
- \*\* VTE: Venous thromboembolic events, defined as deep vein thrombosis (DVT) and pulmonary embolism (PE) (fatal and non-fatal).
- a. Reviewed and adjudicated by an independent Cardiovascular Adjudication Committee in a blinded manner.

